For the Secondary Objectives of Special Interest, change from baseline in SHAPS total score at Week 6 will be compared between JNJ-55308942 [C] mg once-daily and placebo in an ANCOVA model. The model will include intervention (placebo or JNJ-55308942), BD type (I or II), country, concomitant medication status (no mood stabilizer or antipsychotic, a mood stabilizer alone, an antipsychotic alone, or a combination of a mood stabilizer and an antipsychotic), P2RX7 GoF SNP genotype (homozygous or heterozygous) as factors, and baseline SHAPS total score as a covariate. Comparison between JNJ-55308942 [C] mg once-daily and placebo will be performed using appropriate contrasts. Change from baseline in MADRS total score at Week 6 will be assessed with confidence intervals in subgroups for BD type (I or II), P2RX7 GoF SNP genotype (heterozygous or homozygous), and patients with specific biomarker profiles (yes or no) using a similar MMRM as the one used for the primary endpoint analysis.

For other Secondary Objectives, similar MMRM analyses will be conducted for changes in T-score of PROMIS – Ability to Participant in Social Roles and Activities, the PHQ-9 total score, and the GAD-7 total score. Subgroup analyses by mRNA transcript (P2RX7 and IL-1 β) level status at baseline (yes or no) and use of concomitant medication (no mood stabilizer or antipsychotic, a mood stabilizer alone, an

antipsychotic alone, or a combination of a mood stabilizer and an antipsychotic) will also be assessed with confidence intervals using a similar MMRM.

For the CGI-S efficacy endpoint, a frequency distribution of severity scores will be provided by treatment group from Week 1 to Week 6. In addition, frequency of shifting scale at Week 6 from baseline will be provided.

Descriptive statistics will be provided for the SAWB assessments.

Safety Analyses

Statistical analysis of the safety data will be done by the sponsor or under the authority of the sponsor. Specific details will be provided in the statistical analysis plan (SAP).

All safety analyses will be performed based on the safety analysis set, which will include all randomized participants who receive at least 1 dose of study intervention. Safety summaries will be provided by treatment, unless specified otherwise.

Adverse Events

The verbatim terms used in the case report form (CRF) by investigators to identify adverse events will be coded using the Medical Dictionary for Regulatory Activities (MedDRA). Any AE occurring at or after the initial administration of study intervention through the day of last dose plus 30 days is considered to be treatment emergent. All reported treatment-emergent adverse events will be included in the analysis. For each adverse event, the percentage of participants who experience at least 1 occurrence of the given event will be summarized by intervention group. In addition, comparisons between intervention groups will be provided if appropriate.

Summaries, listings, datasets, or participant narratives may be provided, as appropriate, for those participants who die, who discontinue intervention due to an adverse event, or who experience a severe or a serious adverse event.

Clinical Laboratory Tests

Laboratory data will be summarized by type of laboratory test. Reference ranges will be used in the summary of laboratory data. Descriptive statistics will be calculated for each laboratory analyte at baseline and at each scheduled time point. Changes from baseline results will be presented in pre- versus post-treatment cross-tabulations (with classes for below, within, and above normal ranges).

Electrocardiogram (ECG)

Electrocardiogram data will be summarized by ECG parameter. Descriptive statistics will be calculated at baseline and for observed values and changes from baseline at each scheduled time point. Frequency tabulations of the abnormalities will be made.

The ECG variables that will be analyzed are heart rate, PR interval, QRS interval, QT interval, and corrected QT (QTc) interval using [some or all of] the following correction methods: QT corrected according to Bazett's formula (QTcB) and QT corrected according to Fridericia's formula (QTcF).

Descriptive statistics of QTc intervals and changes from baseline will be summarized at each scheduled time point. The percentage of participants with QTc interval >450 msec (males), >470 (females), >480 msec, or >500 msec will be summarized, as will the percentage of participants with QTc interval increases from baseline >30 msec or >60 msec. Also, descriptive statistics of QTc will be provided by gender.

Vital Signs

Descriptive statistics of body temperature, pulse/heart rate, supine blood pressure, and respiratory rate values and changes from baseline will be summarized at each scheduled time point. The percentage of participants with values outside clinically relevant limits will be summarized.

Physical Examination

Abnormalities observed during the physical examination will be summarized and listed by treatment group at each scheduled time point.

Young Mania Rating Scale (YMRS)

Exploratory analyses will be performed for changes from baseline in YMRS total score and for changes from baseline in individual YMRS items by treatment group for all participants receiving at least 1 dose of study intervention. Details will be provided in the SAP.

Columbia Suicide Severity Rating Scale (C-SSRS)

Results from the C-SSRS will be tabulated by treatment group for all participants receiving at least 1 dose of study intervention.

[figure not shown]
Interim analysis

No interim analysis is planned.

It may be recommended that an unblinded data review needs to be performed by an independent reviewer (e.g., data review committee) if deemed critical by the Janssen clinical team. Committee membership responsibilities, authorities, and procedures will be documented in a charter.

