The participant must be symptomatic as assessed using the 17-item Hamilton Depression Rating Scale (HDRS₁₇). Symptom intensity over the past week will be evaluated. Participants who are enrolled in the study will continue on their current medication regimen, if applicable, throughout the study. No dose changes are permitted from screening through the end of the study (until after the follow-up visit). No concurrent use of antidepressants will be allowed (until after the follow-up visit).

For each participant, the study will consist of 3 phases: a screening phase of up to 4 weeks, a double-blind treatment phase of 6 weeks, and a post-treatment follow-up phase of up to 2 weeks (Figure 1). Participants will enter the treatment period where they will be randomly assigned to daily dose administration with **C** mg JNJ-55308942 or placebo for 6 weeks, Day 1 up to and including the last treatment visit, Day 43 +/- 1 day. The study drug should be taken by the participant at every clinic visit during the treatment period. Between approximately 1 to 2 weeks after administration of the last dose, participants will return to the study site for a follow-up visit. The total study duration for each participant will be up to 12 weeks. There will be 7 scheduled visits to the study site during the study, including screening, and follow-up visit.

For study visits, a window of ± 1 day will be allowed.

No study-specific screening procedures will be undertaken prior to finalization of the informed consent form (ICF) procedures and the provision of written informed consent by the participant.

Eligibility Screening Examination (for all study participants)

After giving written consent for screening, participants will be screened between 28 days and 1 day prior to the double-blind treatment phase to ascertain their eligibility for the study according to the inclusion and exclusion criteria. Although the screening period allows for up to 4 weeks, shorter screening periods are encouraged when possible. The assessments scheduled during the screening visit may be divided over multiple days, according to operational and/or site/country-specific needs.

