An additional optional pharmacogenomic blood sample will be collected from enrolled participants on Day 1 to identify genetic factors that may influence the PK, PD, efficacy, safety and/or tolerability of JNJ-55308942 and to identify genetic factors associated with BD. If collection on Day 1 is not feasible, it can be collected on any other visit during the double-blind treatment phase.

SAFETY EVALUATIONS

Adverse events (AEs) will be reported by the participant (or, when appropriate, by a caregiver, surrogate, or the participant's legally acceptable representative) from obtaining the screening informed consent through the day of last dose plus 30 days. There are no AEs of special interest.

The following safety assessments will be performed: physical examination, body weight, vital signs (including oral, tympanic or temporal temperature, blood pressure, pulse/heart rate and respiratory rate), 12-lead electrocardiogram (ECG), urine drug testing, alcohol breath test, pregnancy testing (female participants only), hormones, and clinical labs (hematology, chemistry panel and urinalysis) as per SoA. In addition, serology and hemoglobin A1c (HbA1c) assessments will be performed at screening only.

Emergence of mania will be assessed using the YMRS at each visit.

Emergence of suicidal ideation will be assessed using the C-SSRS at screening and during each visit. The Digital Health Assessment app will alert the investigator when a participant has indicated that the depression is 'much worse' or 'very much worse' when answering weekly questions on depression.

STATISTICAL METHODS

Sample Size

The estimated sample size of 164 participants (82 participants per group) was determined based on the assumption of an effect size of at least 0.45 for the MADRS total score (difference in mean change from baseline at Week 6 between the JNJ-55308942 and placebo groups of 3.9 units with a standard deviation of 8.6). This is considered to be a clinically relevant difference in a population with BD types I or II. The standard deviation of 8.6 in the change in MADRS total score from baseline is a reasonable assumption based on data in a published phase 3 study of quetiapine in BD type I and type II depression (Calabrese 2005). Power is set at 90%, with a 1-sided alpha of 0.10 and a 6-week drop-out rate of 20%. The estimated number of completers to be included in the primary analysis is 132.

Efficacy Analyses

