1.3. Schedule of Activities (SoA)

Phase	Screening	Double-blind treatment phase							Follow-up or EW^h (7 to 14 days after last study visit)
		1	2	3	4	5	6	7	
Visit number ^a	1								
Week (end of)	-4 to 0	0	1	2	3	4	5	6	7/8
Study Day	-28 to -1	1	8	15	22	29	36	43	49-56
Visit window			± 1 day	± 1 day	± 1 day	± 1 day	± 1 day	± 1 day	
Clinic Visit	C	C	C	C	C	C	C	C	
Screening/Administrative									
Informed consent ^b	X								
MINI interview with Borderline Personality Disorder module	X								
ATHF-SF	X								
Inclusion/exclusion criteria	X	X ^{n ad}							
Prestudy therapies	X								
Medical history and demographics	X								
Download and install/register Digital Health Assessment app ^{q,r,c}	X	X							
Safety Assessments									
Physical examination	X	X						X	X
Height	X								
Body weight	X	X						X	X
Urine Drug Screen ^{ab}	X ^m	X	X	X		X		X	X
Alcohol Breath Test	X	X						X	
Pregnancy test ^d	X	X	X	X		X		X	X
Vital signs (supine blood pressure, heart rate, tympanic or oral temperature, respiratory rate)	X	X ⁿ	X ^e	X ^e		X ^e		X ^e	X
12-lead ECG ^g	X	X ⁿ	X ^e	X ^e		X ^e		X ^e	X
YMRS	X	X ^w	X ^u	X ^u		X ^u		X ^u	
C-SSRS ^f	X	X ^w	X ^u	X ^u		X ^u		X ^u	X
Study Intervention Administration									
Randomization		X							
Dispense study intervention		X		X		X			
Oral dose study intervention ^{i,j}		Day 1 up to and including Day 43 ⁱ ± 1 day							
Study intervention accountability by the site		X		X		X		X	

Phase	Screening	Double-blind treatment phase							Follow-up or EW^h (7 to 14 days after last study visit)
		1	2	3	4	5	6	7	
Visit number^a		1	2	3	4	5	6	7	
Week (end of)	-4 to 0	0	1	2	3	4	5	6	7/8
Study Day	-28 to -1	1	8	15	22	29	36	43	49-56
Visit window			1 day	1 day	1 day	1 day	1 day	1 day	
Clinic Visit	C	C	C	C		C		C	
Blood and Urine Collection^m									
Clinical Laboratory tests: Hematology, serum chemistry and urinalysis	X	X		X		X		X	X
Serology, HbA1c	X ^{ac}								
Blood sample collection for PK JNJ-55308942		X ^l	X ^l	X ^l		X ^l		X ^l	
Blood samples for other biomarkers ^k		X		X		X		X	
Blood for research samples (TruCulture) ^x		X						X	
Blood for research sample (PBMCs) ^y		X							
Blood samples for hormones (males only) ^v		X				X		X	X
Blood sample for Pharmacogenomics (general SNPs) ^{aa}		X							
Blood sample for GoF and LoF SNPs (P2X7)	X								
Blood sample for RNA		X ^k				X ^k		X ^k	
Clinician-Administered Assessments									
Structured Interview Guide for HDRS ₁₇ (SIGH-D)	X	X ^p							

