Placebo-control reminder script (PCRS)		X ^l	X	X		X		X	
Structured Interview Guide for MADRS (SIGMA)		X ^l	X	X		X		X	
CGI-S		X ^l	X	X		X		X	
Participant Self-Rating Assessments									
SHAPS		X ^l						X	
PROMIS-Ability to Participate in Social Roles and Activities		X ^l	X	X	X	X	X	X	
PHQ-9		X ^l	X	X	X	X	X	X	
GAD-7		X ^l		X		X		X	
SAWB ^o			X-----X						
Ongoing Participant Review									
Concomitant therapy									Continuous
Adverse events									Continuous

Footnotes:

- a) The procedures scheduled during the screening visit may be divided over multiple days, according to operational and/or site/country-specific needs. A \pm 1 day window will be allowed for study days 8, 15, 22, 29, 36 and 43.
- b) Must be signed before first study-related activity.
- c) The use of the digital health assessment app is mandatory.
- d) Performed for women of childbearing potential (WOCBP). Serum (β -hCG) pregnancy test performed at Screening. At all other time points, urine pregnancy test will be done. If positive, a serum β -hCG test will be performed. Investigators may perform additional pregnancy testing at their discretion as clinically needed.
- e) 12-lead ECG and vital signs will be taken predose of study intervention.
- f) There are 2 versions of the C-SSRS. A “baseline/screening” version will be conducted at screening. A “since your last visit” version will be conducted predose on visit 2, 3, 4, 5, and 6, at follow-up/early withdrawal.
- g) 12-lead ECG should be performed in triplicate at screening.
- h) If a participant discontinues study intervention before the end of the double-blind phase, early withdrawal (EW) visit should be completed.
- i) Study intervention will be taken at home in the morning at approximately the same time (\pm 4 hours) each day, 30 minutes after the start of breakfast (maximum of 2 hours after the start of breakfast). Recommended to take each dose of study intervention with a glass of water.
- j) On study visits 3, 4, 5, and 6, study intervention will be administered at the study site. The participants are instructed to eat at home and come to the site within an hour or less after completion of the meal. Inability to comply with these instructions would not constitute a protocol violation but the patients are encouraged to comply with these instructions. Dosing should be witnessed by the study staff when study intervention is taken at the study site.

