8.1.4. Follow-up or Early Withdrawal Visit (Visit 7)

All participants will have to complete Visit 7 (final follow-up visit or early withdrawal visit). Participants who prematurely withdraw from the study are encouraged to complete Visit 7. During Visit 7, all assessments will be completed per the SoA.

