8.6.6. Suicidal Ideation and Behavior Risk Monitoring

8.6.6.1. Young Mania Rating Scale (YMRS)

The YMRS is one of the most frequently utilized rating scales to assess manic symptoms ([Young 1978](#)). The scale has 11 items and is based on the patient's subjective report of his or her clinical condition over the previous 48 hours. Additional information is based upon clinical observations made during the clinical interview. The items are selected based upon published descriptions of the core symptoms of mania. There are 4 items (irritability, speech, thought content, and disruptive/aggressive behavior) that are graded on a 0 to 8 scale, while the remaining 7 items are graded on a 0 to 4 scale. These 4 items are given twice the weight of the others to compensate for poor cooperation from severely ill patients. There are well described anchor points for each grade of severity. The YMRS total score, with range of 0 to 60, is the sum of each of the 11 individual scores, with higher total YMRS scores reflecting greater symptom severity.

The scale is generally performed by a qualified clinician or other qualified trained rater with expertise with manic patients and takes 15 to 30 minutes to complete.

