	Double-Blind	2	Baseline	≤1	1
		3	Week 1	[2,11]	8

CONFIDENTIAL – FOIA Exemptions Apply in U.S.

12

Table 2: Visit Windows

Parameter	Analysis Phase	Scheduled Visit Number	Time Interval (Label on Output)	Time Interval (Day)*	Target Time Point (Day)*
		4	Week 2	[12,21]	15
		5	Week 4	[22,35]	29
		6	Week 6	≥36	43

^{*}Relative to Study Day 1; FU/EW = Follow-up/Early Withdrawal

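### No YMRS is scheduled at the follow-up/early-withdrawal visit, contrary to the synopsis, so a switch between visits that leads to withdrawal, or one after the last dose, may be missing from the YMRS safety data

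*Protocol*

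**What the plan says.** The safety evaluations in the protocol synopsis (Section 1.1) state: "Emergence of mania will be assessed using the YMRS at each visit". The same synopsis counts the visits: "There will be 7 scheduled visits to the study site during the study, including screening, and follow-up visit".

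The SoA (Section 1.3) has adjacent rows for the two psychiatric safety scales. The YMRS row reads "YMRS X X ^w X ^u X ^u X ^u X ^u" and stops at Day 43. The C-SSRS row reads "C-SSRS ^f X X ^w X ^u X ^u X ^u X ^u X", with one further mark in the follow-up/early-withdrawal column. The C-SSRS footnote confirms this: the since-last-visit "version will be conducted predose on visit 2, 3, 4, 5, and 6, at follow-up/early withdrawal". Section 8 lists Days 1, 8, 15, 29 and 43 for both scales together.

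Section 8.1.4 ties the last visit to the table: "During Visit 7, all assessments will be completed per the SoA". Section 8.6.6.1 says the YMRS rests on the patient's report of his or her "condition over the previous 48 hours".

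In SAP Section 5.1.2, Table 2 (where "FU/EW = Follow-up/Early Withdrawal") gives clinical laboratory tests, vital signs, ECG and C-SSRS a separate FU/EW row and ends their Week 6 window before that visit. The YMRS rows end at Week 6, with an open window of Day 36 or later and no FU/EW row.

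**The concern.** YMRS is a named endpoint of the secondary safety objective, and emergence of mania is listed among the key safety assessments. Protocol Section 4.2 gives the risk of a switch as one reason for excluding antidepressants, and Section 2.3.1 notes that the compound has not been given to humans for more than 10 days, nor to patients with bipolar depression.

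The early-withdrawal visit is where a participant who leaves because of a mood change would be seen, and it has no mania rating. A site cannot follow both the synopsis sentence and the SoA. If it follows the SoA, the change-from-baseline tables may lack scores from some of the participants for whom they matter most. Adverse event reports would pick up recognised episodes, but they give no score against baseline and would not show smaller rises.

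**Working it through.** The plan states no figure for this, so the check is a comparison of the schedules plus simple counts.

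**Visits.** Seven site visits are scheduled. YMRS is marked at six: screening and Days 1, 8, 15, 29 and 43. The missing one is Visit 7. C-SSRS is marked at all seven.

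**Spacing and recall.** The gaps between ratings from Day 1 are 8 − 1 = 7, 15 − 8 = 7, 29 − 15 = 14 and 43 − 29 = 14 days. With 48-hour recall, the Day 43 rating reaches back to about Day 41. Suppose a switch begins on Day 34 and the early-withdrawal visit is on Day 36. The last scheduled YMRS is then Day 29, which is 5 days before onset and 7 days before exit. Nothing scheduled at the exit visit rates it.

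**After the last dose.** Follow-up is planned for Days 49 to 56. No YMRS is scheduled after Day 43, so mania first appearing in that interval is not rated in any completer.

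**Number affected.** The sample size section plans 164 participants, 20% drop-out and 132 completers. Early leavers: 164 − 132 = 32 (directly, 0.20 × 164 = 32.8). This counts leavers for any reason, including anyone who leaves at or just after a visit where YMRS was done, so it is an upper bound.

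**What the SAP would do with a Visit 7 score.** Adding the SoA mark alone would not be enough. SAP Section 5.1.2 keeps the visit closest to the target day in each window and leaves the others out of summaries and analyses.

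- A completer rated on Day 43 and again on Day 50 has both scores in the YMRS Week 6 window. The distances from target are 0 and 7 days, so the follow-up score is dropped from the tables and survives only in the listing.
- A participant without a Day 43 rating but with a Day 50 rating would have an off-drug score tabulated as Week 6.
- A participant rated on Day 29 and at exit on Day 34 has both scores in the Week 4 window (Days 22 to 35). The Day 29 score is kept and the exit score dropped.

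The SAP version history says version 2.0 closed the Week 6 window before follow-up/early withdrawal for safety assessments. Table 2 does this for laboratory tests, vital signs, ECG and C-SSRS, but not for YMRS.

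**The case against.** The strongest reply is that the schedule is deliberate and the synopsis sentence is loose. The C-SSRS footnote and Section 8.6.6.2 name the follow-up visit, the YMRS section does not, and the latest amendment revised the YMRS timing. This does not settle the matter. The Section 8 day list covers both scales, yet C-SSRS is also done at Visit 7, so the list is not exhaustive. No text explains leaving YMRS out. It does stand that the documents alone do not show which passage was intended.

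A second reply is that the safety objective covers the six-week treatment period and that the YMRS analysis is exploratory and descriptive, with no test or decision rule. This weakens the post-treatment half of the point and means the primary inference is untouched. It does not answer the early-withdrawal half, which falls within the treatment period. C-SSRS serves the same objective and is rated at follow-up.

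A reader might infer that a switch causing withdrawal can never reach the YMRS endpoint. The documents do not support that:

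- A switch present on Day 8, 15, 29 or 43 is scored.
- Protocol Section 7.2 has scheduled assessments continuing after drug is stopped, although Section 7.4 withdraws such participants automatically.
- The SAP does not cut YMRS off at drug stop. Its double-blind analysis phase runs to last contact, so an unscheduled rating could be used, subject to the window rule.
- Mania is collected as an adverse event to 30 days after the last dose, and serious mania is an anticipated event reviewed in aggregate.
- The SAWB items include manic symptoms during treatment, summarised weekly by arm. The described investigator alert, however, concerns worsening depression.

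A reader might also note that four ratings with two-day recall cover 8 of 42 treatment days. That reflects the scale and the visit spacing, not this omission: a Visit 7 rating would not change it for completers.

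**Conclusion.** The contradiction is real. The synopsis promises YMRS at every visit, while the SoA and SAP Table 2 omit it at Visit 7. As scheduled, a switch that arises between visits and leads to withdrawal, or that first appears after the last dose, may be recorded only as an adverse event or, on treatment, through the SAWB, and not in the YMRS data.

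Up to about 32 of 164 participants could leave without a scheduled exit YMRS. The number who would leave with a switch cannot be estimated, because the documents give no switch rate. The withdrawal pathway is also an assumption: Sections 7.2 and 7.4 contain no mania-specific rule, so it would run through the investigator's or sponsor's safety judgement. A claim that the YMRS tables will look falsely reassuring goes beyond the documents; what they show is that the scores are not scheduled. The primary analysis is not affected. The change is worth making because the gap is in a named safety endpoint and costs little to close.

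**What to change.** Reconcile the synopsis, the SoA, Section 8 and SAP Table 2 as follows:

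- Mark YMRS in the follow-up/early-withdrawal column of the SoA, and add that visit to the Section 8 timing text.
- Add a FU/EW row for YMRS in SAP Table 2.
- End the YMRS Week 6 window on the day before FU/EW, as Table 2 already does for C-SSRS, vital signs, ECG and laboratory tests, so that follow-up scores are neither labelled Week 6 nor dropped.

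Sections 7.2 and 7.4 of the protocol must also be reconciled on whether scheduled assessments continue after drug is stopped, since that decides whether an early leaver has any later YMRS.

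Narrowing the synopsis sentence instead would remove the contradiction but leave the gap. The cost of closing it is one SoA mark with its matching text, one SAP row and one window limit, plus the 15 to 30 minutes that Section 8.6.6.1 gives for the scale, at a visit that already takes place and already includes the C-SSRS.
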